#### 7.7 EXTENT OF EXPOSURE

Not all drug administrations are captured in the data base. Thus, no analysis of comprehensive exposure data is planned for the CTR. The date and time of drug administration captured in the eCRF will be listed for each patient.

#### 7.8 SAFETY ANALYSIS

All safety analyses will be performed on the TS.

The safety data for treated patients who failed to complete the study (dropouts or withdrawals) will be reported as far as their data are available. All withdrawals will be documented and the reason for withdrawal recorded.

#### 7.8.1 Adverse Events

AEs will be coded with the most recent version of MedDRA.

Unless otherwise specified, the analyses of AEs will be descriptive in nature. All analyses of AEs will be based on the number of patients with AEs and not on the number of AEs.

For further details on summarization of AE data, please refer to "Analysis and presentation of adverse event data from Clinical Trials" (8) and "Handling of missing and incomplete AE dates" (7).

The analysis of AEs will be based on the concept of treatment emergent AEs.

An overall summary of AEs will be presented. This overall summary will comprise summary statistics for the class of AESIs.

**CTP:** *The following are considered as AESIs:* 

#### Hepatic injury

A hepatic injury is defined by the following alterations of hepatic laboratory parameters:

- an elevation of AST (Aspartate Aminotransferase) and/or ALT (Alanine Aminotransferase) ≥3 fold ULN combined with an elevation of total bilirubin ≥2 fold ULN measured in the same blood draw sample, or
- aminotransferase (ALT, and/or AST) elevations  $\geq$ 10 fold ULN.

The investigator had to classify on the eCRF whether an observed AE was an AESI or not.

According to ICH E3 (9), in addition to Deaths and Serious Adverse Events, 'other significant' AEs need to be listed in the CTR. These will be any non-serious adverse event that led to an action taken with study drug (e.g. discontinuation).

The frequency of patients with AEs will be summarised by treatment, primary system organ class (SOC) and preferred term (PT). AEs which were considered by the investigator to be drug related will be summarised separately. A listing will be provided for patients with AEs, where SAEs, drug-related AEs, AEs leading to drug withdrawal and AESIs will be presented in the listing.

The SOCs and preferred terms within SOCs will be sorted by descending frequency over all treatment groups.

For disclosure of AE data on ClinicalTrials.gov, the frequency of patients with non-serious AEs occurring with an incidence of greater than 5 % (in preferred terms) will be summarised by treatment, primary SOC and preferred term. The frequency of patients with SAEs will also be summarised.

For disclosure of AE data in the EudraCT register, the frequency of AEs, the frequency of non-serious AEs with an incidence of greater than 5 % (in preferred terms) and the frequency of SAEs will be summarized.

For support of lay summaries, the frequency of patients with drug-related SAEs will be summarized by treatment, primary SOC and preferred term.

# 7.8.2 Laboratory data

The analyses of laboratory data will be descriptive in nature and will be based on BI standards "Display and Analysis of Laboratory Data" (10).

Analyses will be based on normalised values, which means transforming to a standard unit and a standard reference range. The original values will be analysed if the transformation into standard unit is not possible for a parameter.

Listings of laboratory values over time and for the difference from baseline (refer to Section 6.7) will be provided. Values outside the reference range as well as possibly clinically significant values will be flagged in the listings.

Individual line plots over time by dose group will be presented.

Clinically relevant findings in laboratory data will be reported as baseline conditions (when they occurred prior to first administration of study treatment) or as AEs (when they occurred after first administration of study treatment) if judged clinically relevant by the investigator, and will be analysed as such.

# 7.8.3 Vital signs

Vital signs will be analysed based on treatment groups, as defined in Table 6.1: 1. Listings of each parameter over time and for the difference from baseline (refer to Section 6.7) will be provided.

TSAP for BI Trial No: 1405-0008

Proprietary confidential information © 2022 Boehringer Ingelheim International GmbH or one or more of its affiliated companies

# **7.8.4** ECG

12-lead ECG recordings will be checked by the investigator for pathological results. Clinically relevant abnormal findings for ECG will be reported either as baseline condition (when they occurred before intake of first study treatment) or will be reported as AEs (when they occurred after first administration of study treatment) and will be summarized as such.

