Investigator-defined drug-related AEs were reported for 12 (18.5%) of 65 subjects treated with BI 1323495 and 1 (4.5%) of 22 subjects receiving placebo. Headache of mild intensity was the most frequently reported drug related AE (by 6 subjects treated with BI 1323495). Abdominal pain was reported by 3 subjects treated with BI 1323495, the furthergastrointestinal events abdominal pain diarrhea and flatulence each in 2 subjects treated with BI 1323495 and CK elevation was reported for 1 subject. No other drug related AEs were reported in more than one subject treated with BI 1323495. One subject in the placebo group had an AE of severe intensity (abdominal discomfort) that was considered related. One EM subject in the 30 mg dose group had an AE of severe intensity (headache; not considered related to study medication). All other reported AEs were of mild or moderate

Boehringer Ingelheim		22 Apr 2021
BI Trial No.: 1405-0008		
c31693972-02	Clinical Trial Protocol	Page 31 of 111

intensity. Overall, three AEs led to treatment discontinuation: One each in the EM dose groups 30 mg bid (nausea/vomiting, moderate, not considered related), 70 mg bid (blood pressure increased, moderate, considered related), and 150 mg bid (electrocardiogram QT prolonged, mild, considered related). There was no apparent relationship of the occurrence of AEs with dose. An overview on AEs judged related by the investigator is presented in Table 1.2.3.3: 1. In summary, multiple doses of BI 1323495 investigated so far in clinical trials with healthy subjects were safe and well tolerated.

Boehringer Ingelheim		22 Apr 2021
BI Trial No.: 1405-0008		
c31693972-02	Clinical Trial Protocol	Page 32 of 111
Proprietary confidential information	© 2021 Boehringer Ingelheim International GmbH or one or	more of its affiliated companies

Table 1.2.3.3: 1: Drug-related AEs reported in MRD trial 1405-0002

System Organ Class	Placebo		BI 1323495								
			Ex	tensive m	etabolize	rs				Total on	Total on
Preferred Term				(EN	/ls)			Poor meta	abolizers (PMs)	BI 1323495	treatment
		10 mg	30 mg	70 mg	120 mg	150 mg	120 mg				
		bid	bid	bid	bid	bid	qd	10 mg	30 mg		
Number of subjects, N (%)	22 (100)	9 (100)	9 (100)	9 (100)	9 (100)	9 (100)	9 (100)	5 (100)	6 (100)	65 (100)	87 (100)
Total with any drug related AEs	1 (4.5)	2 (22.2)	3 (33.3)	1 (11.1)	2 (22.2)	4 (44.4)	0 (0)	0 (0)	1 (16.7)	11(16.9)	12 (13.8)
Gastrointestinal disorders/											
Abdominal discomfort	1 (4.5)										1 (1.1)

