Abdominal pain	1 (4.5)					1 (11.1)			1 (16.7)	2 (3.1)	3 (3.4)
Abdominal pain (upper)						1 (11.1)				1 (1.5)	1 (1.1)
Diarrhea			1 (11.1)			1 (11.1)				2 (3.1)	2 (2.3)
Flatulence			1 (11.1)			1 (11.1)				2 (3.1)	2 (2.3)
Investigations/											
Blood pressure increased				1 (11.1)						1 (1.5)	1 (1.1)
CK elevation					1 (11.1)					1 (1.5)	1 (1.1)
Electrocardiogram QT prolonged						1 (11.1)				1 (1.5)	1 (1.1)
Electrocardiogram PR shortened					1 (11.1)					1 (1.5)	1 (1.1)
Nervous system disorders/											
Headache		1 (11.1)	3 (33.3)	1 (11.1)		1 (11.1)				6 (9.2)	6 (6.9)
Syncope		1 (11.1)								1 (1.5)	1 (1.1)

Boehringer Ingelheim		22 Apr 2021
BI Trial No.: 1405-0008		_
c31693972-02	Clinical Trial Protocol	Page 33 of 111

In the ongoing DDI study 1405-0015, 14 healthy male subjects were administered single doses of rosuvastatin, and of BI 1323495 300 mg in combination with rosuvastatin. Any AEs were reported in 5 of the 14 subjects (35.7%) while treated with BI 1323495 and rosuvastatin, and in 4 of the 14 subjects (28.6%) while treated with rosuvastatin alone. Investigator-defined drug related AEs were reported for 2 (14.3%) of the 14 subjects, both while treated with rosuvastatin alone. No severe or serious AEs were reported.

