5.2.4 Electrocardiogram

The 12-lead ECGs must be administered by a qualified technologist and results will be recorded as scheduled in the Flow Chart. The investigator or a designee will evaluate whether the ECG is normal or abnormal and assess clinical relevance. ECGs may be repeated for quality reasons and a repeated recording used for analysis.

Additional ECGs may be recorded for safety reasons. Dated and signed printouts of ECG with findings should be documented in patient's medical record.

Clinically relevant abnormal findings will be reported either as baseline condition (if identified at the screening visit) or otherwise as AEs and will be followed up and/or treated as medically appropriate.

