7.2.5 Safety analyses

Adverse events will be coded using the Medical Dictionary for Drug Regulatory Activities (MedDRA). Standard BI summary tables and listings will be produced. All adverse events with an onset between start of treatment and end of the REP, a period of 7 days after the last dose of trial medication, will be assigned to the on-treatment period for evaluation. For all analyses the treatment actually administered (= treatment at onset) to the patient will be used (any deviations from the randomised treatment will be discussed in the minutes of the Report Planning Meeting).

All treated patients will be included in the safety analysis. In general, safety analyses will be descriptive in nature and will be based on BI standards. No hypothesis testing is planned.

Statistical analysis and reporting of adverse events will concentrate on treatment-emergent adverse events, i.e. all adverse events occurring between start of treatment and end of the REP, see Section 1.2.4. Adverse events that start before first drug intake and deteriorate under treatment will also be considered as 'treatment-emergent'.

Frequency, severity, and causal relationship of adverse events will be tabulated by system organ class and preferred term after coding according to the current version of the Medical Dictionary for Drug Regulatory Activities (MedDRA) at database lock.

Boehringer Ingelheim		22 Apr 2021
BI Trial No.: 1405-0008		
c31693972-02	Clinical Trial Protocol	Page 82 of 111

Laboratory data will be analysed both quantitatively as well as qualitatively. The latter will be done via comparison of laboratory data to their reference ranges. Values outside the reference range as well as values defined as clinically relevant will be summarised. Treatment groups will be compared descriptively with regard to distribution parameters as well as with regard to frequency and percentage of patients with abnormal values or clinically relevant abnormal values.

Vital signs, physical examinations, or other safety-relevant data observed at screening, baseline, during the course of the trial and at the end-of-trial evaluation will be assessed with regard to possible changes compared to findings before start of treatment.

Clinically relevant abnormal findings in ECG will be reported either as baseline condition (at screening) or otherwise as AEs.

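### ECG intervals get no by-group summary, although QT prolongation was one of the two drug-related treatment stops in the multiple-dose trial

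*SAP*

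**What the plan says.** **ECG.** SAP 7.8.4 states that "12-lead ECG recordings will be checked by the investigator for pathological results". Findings judged clinically relevant become baseline conditions if present before the first dose and adverse events afterwards. Protocol 7.2.5 agrees: "Clinically relevant abnormal findings in ECG will be reported either as baseline condition (at screening) or otherwise as AEs". Protocol 5.2.4 describes what the site does: "The investigator or a designee will evaluate whether the ECG is normal or abnormal and assess clinical relevance". It names no interval measurement, yet it also says "ECGs may be repeated for quality reasons and a repeated recording used for analysis". Footnote 2 of the Sample and Assessment Flow Chart specifies single recordings without a central laboratory. SAP 6.7 handles ECG findings as adverse event data outside the visit-based analysis, and its tables of analysis windows cover laboratory data and spirometry only. Protocol 5.7, however, says that the schedule permits changes in ECG parameters to be monitored.

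**Background.** On the multiple-rising-dose trial, Protocol 1.2.3.3 reports: "Overall, three AEs led to treatment discontinuation: One each in the EM dose groups 30 mg bid (nausea/vomiting, moderate, not considered related", then "70 mg bid (blood pressure increased, moderate, considered related), and 150 mg bid (electrocardiogram QT prolonged, mild, considered related".

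**Vital signs.** SAP 7.8.3 says that they are analysed by treatment group and then names one output: "Listings of each parameter over time and for the difference from baseline". SAP 6.1 also says that they are analysed by dose group, separating baseline from on-treatment values.

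**The concern.** The primary objective is to compare safety and tolerability with placebo. This is the first dosing in patients, up to age 80, and it lasts 12 weeks against 10.5 or 11 days in the earlier trial. The results are meant to help set the regimen for later studies. QT prolongation is one of the two events that the investigators linked to the drug and that ended treatment.

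The plan reduces every ECG to one site reader's judgement of clinical relevance. If QTc rose modestly in many patients, or markedly in one whose site did not call it relevant, the report could truthfully state that there were no ECG adverse events while the recordings showed a difference between groups. Nobody would see that difference, because no group-level interval result is specified.

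**Working it through.** **1. ECGs per patient** (main flow chart; Sample and Assessment Flow Chart). V1: 1. V3: 2 (pre-dose, 6 h). V5: 1. V6: 2 (pre-dose, 6 h). V8: 1. V10: 1. Follow-up visit V11: vital signs only. Total 8. After the first dose: V3 6 h, V5, V6 pre-dose, V6 6 h, V8, V10 = 6. For 36 patients: 8 × 36 = 288 recordings, and 6 × 36 = 216 after the first dose.

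**2. Group sizes** (Protocol 7.4 and 7.5). A 3:1 ratio in 12 gives 9 + 3, and in 24 gives 18 + 6. Placebo is 3 + 6 = 9, and the total is 9 + 18 + 9 = 36, as stated.

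**3. The earlier events** (Protocol 1.2.3.3, text and table). Three adverse events led to stopping, and two were considered related. "Electrocardiogram QT prolonged" occurred in 1 of 9 at 150 mg bid (11.1%), which is 1 of 65 on active drug (1.5%). The text identifies it as a QTcB prolongation. One PR shortening at 120 mg bid was also considered related.

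**4. What an adverse event count can show.** The chance of at least one such event in n patients is 1 − (1 − p)^n. The two rates are illustrations taken from step 3.

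| True rate p | 18 on 150 mg qd | 9 on 30 mg bid |
|---|---|---|
| 1/65 | 24% | 13% |
| 1/9 | 88% | 65% |

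At the lower rate, a report of no ECG events is the likely result whether or not the drug causes them.

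**5. What a table of mean change could show.** The 95% half-width is t(0.975, n1 + n2 − 2) × SD × √(1/n1 + 1/n2). The documents give no SD, so 10 to 20 ms is assumed. For 18 against 9: 2.06 × 0.408 × SD = 0.841 × SD.

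| Comparison | SD 10 | SD 15 | SD 20 |
|---|---|---|---|
| 150 mg qd (18) vs pooled placebo (9) | 8.4 ms | 12.6 ms | 16.8 ms |
| 150 mg qd (18) vs Part B placebo (6) | 9.8 ms | 14.7 ms | 19.6 ms |
| 30 mg bid (9) vs pooled placebo (9) | 10.0 ms | 15.0 ms | 20.0 ms |
| 30 mg bid (9) vs Part A placebo (3) | 14.9 ms | 22.3 ms | 29.7 ms |

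**6. Timing.** The only fixed post-dose ECG time is 6 h. In the food effect trial, the fed median tmax was 2.00 h (Protocol 1.2.3.1). A mean at 6 h therefore does not describe the effect at peak.

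**The case against.** **The prior signal is weak, and this stands.** There was one mild case, on a regimen not used here. Protocol 1.2.3.3 reports no apparent relationship of adverse events to dose, no drug-related events among 9 subjects at 120 mg qd, and no clinically relevant ECG changes after single doses up to 600 mg. The hERG IC50 of 80 µM is 80,000/362, or about 221 times, the highest geometric mean steady-state Cmax in the multiple-dose table. This limits the urgency. It is not a reason to leave scheduled recordings unsummarised.

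**Safety is covered by other routes, and this stands in part.** Clinically relevant ECG changes are adverse events tabulated by treatment, and they count in the primary endpoint if judged drug-related. The sponsor also reviews unblinded safety data periodically (Protocol 7.2.7). Neither route specifies an interval summary. The company reporting standards that the SAP cites are not available to us, and parts of the public SAP are missing, but 7.8.3 and 7.8.4 read as complete.

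**Stronger readings that the documents do not support.**
- A reader might infer that blood pressure, the other drug-related stop, is only listed and that a shift would go unreported. SAP 6.1 and 7.8.3 say that vital signs are analysed by group, SAP 7 sets descriptive statistics for continuous variables, and differences from baseline are listed. What is missing is the name of a table.
- A reader might infer that ECG intervals would not even be listed. SAP 7 says that individual values of all patients are listed, which would include intervals if they are captured. The documents do not say whether they are.
- A reader might expect an interval table to rule out a large shift. It cannot be relied on for that: the SDs are assumed, SAP 6.1 makes pooling of placebo optional, the ECGs are single and site-read, and the fixed time is 6 h.

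**Protocol and SAP agree, and the trial is exploratory.** That is true. This is a better use of recorded data, not a contradiction or an error in the primary analysis.

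**Conclusion.** The gap is real and confined to ECG intervals. With 216 recordings planned after the first dose, the plan specifies no by-group QTc or PR result, so a shift or outlier below the site's threshold of clinical relevance would appear in none. The primary endpoint is unaffected.

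The gain from a table is modest: about 8 to 17 ms half-width for 150 mg qd against pooled placebo, and wider if placebo is split by part. These widths rest on an assumed SD of change of 10 to 20 ms and on full enrolment with complete recordings. The event chances in step 4 assume that rates from short dosing in healthy volunteers carry over to patients. The point is worth acting on because the change is cheap, not because the earlier case establishes a QT effect.

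**What to change.** In SAP 7.8.4, add one descriptive table by treatment group, with placebo shown by part and pooled:
- QTcF, PR and heart rate, as value and as change from the V3 pre-dose recording;
- V3 6 h, V5, V6 pre-dose, V6 6 h, V8 and V10 as separate time points. The laboratory windows in SAP 6.7 should not be reused, since they would place V3 6 h in the Week 2 window and merge the two V6 recordings;
- counts of patients in standard QTcF value and change categories at any on-treatment ECG.

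State that the table is descriptive and that the 6 h recording does not address peak concentration. Keep the investigator-judged adverse event reporting as it is.

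State whether the intervals are in the eCRF. If they are, the cost is a SAP revision (the plan was final on 15 September 2022) and one table. If not, the intervals must be transcribed from printouts: 7 per patient (V3 pre-dose plus the 6 later recordings), so up to 7 × 36 = 252. Protocol 5.2.4 leaves some doubt whether every printout is kept or only those with findings, so this should be confirmed with the sites first.

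In SAP 7.8.3, name a by-group value and change table for blood pressure and pulse rate. This only clarifies what the section already implies.

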#### **7.8.5** Others

Physical examination findings will be reported as relevant medical history/baseline condition (i.e., a condition already existent before intake of first study treatment) or as AE (after first administration of study treatment) and will be summarized as such.

TSAP for BI Trial No: 1405-0008 Page 23 of 25

Proprietary confidential information © 2022 Boehringer Ingelheim International GmbH or one or more of its affiliated companies

#### **10. HISTORY TABLE**

History table Table 10: 1

Version	Date	Author	Sections changed	Brief description of change
Final	15 SEP 2022		None	This is the final TSAP
